### PRINCIPAL INVESTIGATOR: [name] Shirley Ryan AbilityLab [name] [contact]

#### **VERSION NUMBER: 7**

#### VERSION DATE: January 8, 2019

#### **OBJECTIVES:**

Aim 1: Determine the capability of an anti-serotonergic agent to reduce hyperexcitability poststroke without compromising voluntary strength.

Aim 2: Assess the efficacy of using a multimodal intervention combining an antimonoaminergicagent with upper extremity training.

Hypothesis: We investigators hypothesize that the group receiving the combined cyproheptadine and active movement therapy will have better outcomes than the groups receiving passive therapy or placebo.

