#### BACKGROUD:

Chronic sensorimotor impairment of the upper extremity is prevalent in more than 6 million stroke survivors in the U.S. (Go, et al., 2013), especially in the distal upper extremity (Trombly, 1989). In our studies of the impairment mechanisms of hand motor control after stroke, e.g., (Cruz, et al., 2005; Kamper, et al., 2006; Triandafilou, et al., 2011), we have been struck by two phenomena which arise following the original brain lesion; i) involuntary hyperexcitability of the motor units in certain muscles and ii) the difficulty in producing and controlling voluntary muscle activation. We propose to directly treat both of these phenomena simultaneously in order to improve motor control of the hand and arm. We will reduce motoneuronal hyperexcitability through administration of an anti-serotonergic drug which does not increase weakness, and we will guide the generation of proper muscle activation with a custom device and computer program. We believe that our multimodality treatment approach is innovative in that we combine the use of pharmacological agents with individualized movement therapy in a manner that can be used with patients with poor initial motor control. In separate preliminary studies, we were able to show that a single dose of the agent cyproheptadine could reduce unwanted muscle excitation without decreasing voluntary strength (Seo, et al., 2011) and that active motor training, assisted by an electromyographically (EMG) controlled actuated glove, could lead to statistically significant improvement both in measures of impairment and task performance. In this study, we will combine these approaches to create a novel treatment paradigm for improving motor control of the distal upper extremity after stroke. These techniques are amenable to rapid and widespread integration into the clinic for the arm and hand, and could be applied to the lower extremity as well.

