### Outcome Measures:

Subjects will be tested at the Arms and Hands Lab at baseline and the end of each week during the titration phase. Thus, data will be collected prior to administration of any agent, after one week at the lowest dosage of up to 8 mg per day, after one week at the next dosage of up to 16 mg per day, and after one week at the highest dosage of up to 24 mg per day. Data from the 4 testing sessions will be used to assess the impact of cyproheptadine on stroke. All outcome measures will be collected during each testing session. Pill counts will be performed each week as well to gauge subject compliance.

**Fig. 6.** Depiction of the interface between the fingers and the device. The motor shaft rotates the U-piece coupled to the proximal phalanges of the fingers. For the spasticity experiments, the proximal and distal interphalangeal joints will be fixed in neutral with finger splints.

Three potential manifestations of motoneuronal hyperexcitability will be quantified: spasticity, excessive coactivation during voluntary contraction, and prolonged muscle relaxation time. Spasticity will be precisely measured using techniques we have successfully employed in the past in which all four fingers are coupled to a servomotor through a custom jig (Fig. 6). Rotation of the servomotor shaft produces equivalent rotation of the MCP joints. The servomotor will impose constantvelocity rotation of the MCP joints in order to stretch the long finger flexors. Fast MCP rotation (300°/s) will be applied to evoke a stretch reflex. Slow MCP rotation (10°/s) will be imposed to measure nominally passive resistance. Wrist orientation and position will be fixed with a fiberglass cast which is subsequently clamped to a table (Fig. 6). MCP angle, angular velocity, and torque are recorded for analysis of spasticity. EMG recordings will be obtained with surface

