## **RISKS TO PARTICIPANTS:**

The primary risks for involvement in this study are associated with the pharmacological agent to be tested. Although cyproheptadine hydrochloride itself is not being used or administered differently than the FDA approved method, it is being used for a potentially different outcome, namely reduced unwanted muscle tone following stroke.

Some of the potential side effects of taking cyproheptadine include: diminished mental alertness, drowsiness, dizziness, hallucinations, insomnia, muscle weakness, chest congestion, headache, hypertension, increased appetite, upset stomach, diarrhea, difficulty urinating, vision problems, skin rash and dry mouth, nose, and throat, and convulsions. Although reported clinical experience has not identified differences in responses between the elderly and younger patients, elderly patients should be more cautious of possible risks. These risks may include decreased hepatic, renal or cardiac function.

To minimize these risks, we will begin with low levels of the drug and gradually titrate (increase) up to the optimal target dose for the study, which is still well within the safe level of this drug. Patients will be evaluated weekly and will be able to contact the study doctor at any time with questions or concerns. As a precautionary measure, liver profiles (requiring blood draws) will be run prior to initiation of drug administration and at the end of week 3 (chronic drug dose) to check drug impact on liver function although liver damage is not a known side effect. Following the medical screening, additional labs may be ordered at the discretion of the study doctor. Adverse events, including falls, will be assessed weekly at minimum.

Additionally, the medication may have side effects when combined with other types of drugs and/or alcohol. Some side effects of taking combined drugs may lead to confusion, high blood pressure, high fevers, tremor or muscle rigidity, and increased activity.

The effects of the study drug, cyproheptadine, on human sperm and eggs have not been studied and are therefore unknown. The effects of cyproheptadine in humans have not shown to cause negative conditions in either the mother or the fetus during pregnancy.

However, studies in animals have shown an increased risk of birth defects and fetal hormonal imbalances. The effects of this medication in women who are nursing have been shown to produce hormonal imbalances in the newborn.

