Title: Altering Activation Patterns Post-stroke **NCT:** NCT02418949 **Date:** 6/4/2014

Analysis: Spasticity will be quantified using the MCP angular position and torque data from the trials of imposed MCP rotation [27, 66-68]. Namely, the nominally passive torque curve (recorded during the 10°/s trial) will be subtracted from the total torque curve (recorded during the 300°/s). Mean reflex torque will then be computed from the resulting signal by averaging across a 300-ms period beginning at the end of stretch. The EMG data, normalized by the values recorded during maximum contraction, will be used to confirm that a reflex occurred. The FDS signal must surpass a threshold of 5% of maximal contraction for classification as a spastic stretch reflex and subsequent evaluation. Coactivation during voluntary tasks will be computed from the ratio of normalized EDC/FDS for flexion and FDS/EDC for extension. Values closer to 0 indicate less coactivation. Relaxation time will be estimated as the elapsed time from cessation of the auditory tone to the FDS signal dropping below a threshold level equal to three standard deviations of the resting signal [34]. Active isometric flexion and extension torque will be found by subtracting the initial, passive torque from the peak torque recorded during the respective trials.

Statistical analyses will be employed to assess the effect of cyproheptadine on these outcome measures. We will perform repeated measures analysis of variance (rmANOVA) with the between-subject factor Drug (cyproheptadine, placebo) and the within-subject factor evaluation Session (pre-administration, week 1, week 2, week 3 - see Fig. 1). To test the first hypothesis, addressing efficacy in reducing hyperexcitability, the measures spastic reflex, FDS relaxation time, and coactivation ratio will be used as dependent variables in a MANOVA. Should evidence of a significant effect appear, i.e., a Wilk's lambda value < 0.05, we will perform subsequent post-hoc ANOVAs to test the effects on individual dependent variables. To examine the second hypothesis, regarding loss of strength, separate rmANOVAs will be conducted for extension and flexion strength. Similarly, as we wish to minimize Type II errors for these potentially negative outcomes, separate rmANOVAs will be run for ESS and BDI-II without correction. Normality of the residuals will be tested for these parametric tests and non-parametric tests will be run if normality assumptions are violated.

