We will have 50 subjects in each of our Drug groups (cyproheptadine/placebo) in accordance with the power analysis performed for the whole study (see *Aim 2: Analysis*). Thus, we will be able to detect an effect size of 0.22 with a power of 80% for an α of 0.05 (G*Power 3.0 software [69]). In our pilot study examining a single dose of cyproheptadine, we observed a much greater effect size of 0.60 for the reduction in relaxation time. Importantly, the targeted subject numbers will allow us to detect even moderate decreases in strength or increases in somnolence.

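### Aim 1 needs a conclusion that strength is preserved, but the supplied SAP text offers only difference tests, names no deciding term and sets no bound on a loss

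*SAP*

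**What the plan says.** The Protocol's Objectives section gives Aim 1 as: "Determine the capability of an anti-serotonergic agent to reduce hyperexcitability poststroke without compromising voluntary strength". The aim has two halves, and the second concerns strength.

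The SAP's only analysis for that half is: "To examine the second hypothesis, regarding loss of strength, separate rmANOVAs will be conducted for extension and flexion strength". The model has a between-subject factor Drug and "the within-subject factor evaluation Session (pre-administration, week 1, week 2, week 3 - see Fig. 1"). If residuals are not normal, a non-parametric test replaces it.

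The SAP's power paragraph adds: "Importantly, the targeted subject numbers will allow us to detect even moderate decreases in strength or increases in somnolence". It states a detectable effect size of 0.22 at 80% power and α of 0.05 with 50 per Drug group. It does not name the effect-size metric or quantify a moderate decrease.

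Two other Protocol passages give context. The Background describes the approach as "administration of an anti-serotonergic drug which does not increase weakness", which is a premise about the drug rather than an objective. The Risks section lists muscle weakness among possible side effects: "drowsiness, dizziness, hallucinations, insomnia, muscle weakness, chest congestion".

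The supplied text does not state an acceptable loss, a confidence-interval criterion, the model term that answers the strength question, or how a non-significant result will be read.

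**The concern.** A test for a difference asks whether a loss has been shown. Aim 1 also needs an answer to another question: how large a loss the data still allow. A non-significant F test, or a non-significant rank test, does not answer that. If both strength tests come out non-significant, the plan gives no route from the result to the second half of the Aim 1 conclusion.

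The unnamed term adds to this. A Drug by Session model yields a Drug main effect and a Drug by Session interaction. The main effect averages over all four sessions, including one before any drug is taken, so it dilutes a drug-induced loss. The interaction looks for a change in the group difference over sessions. The two can give very different answers on the same data, and the choice could be made after the results are seen.

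At stake is the strength half of Aim 1. The primary endpoint (Graded Wolf Motor Function Test time) is not affected.

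**Working it through.** **Inputs from the documents:** 50 per Drug group; four sessions (pre-drug, weeks 1, 2, 3); α 0.05; stated detectable effect size 0.22 at 80% power.

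**Assumptions (not in the documents):** between-session correlation r = 0.5, 0.7, 0.8 or 0.9; compound symmetry; SD = 1 at each session; an illustrative loss of 0.4 SD, which is not a proposed margin.

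**1. The plan's own figure.** Read 0.22 as Cohen's f for the Drug main effect, with N = 100, m = 4 and r = 0.5:

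λ = f²·N·m / (1 + (m−1)r) = 0.22² × 100 × 4 / 2.5 = 7.74, on 1 and 98 df.

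Power is 78.7%, and f at exactly 80% power is 0.224. So 0.22 reproduces as a main-effect figure at r = 0.5. Under the same assumptions the interaction would give f = 0.118. This suggests, but does not prove, that the power statement rests on the main effect. In either case it measures the ability to detect a difference and does not bound a loss.

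**2. Loss of 0.4 SD present at weeks 1 to 3**, d = (0, 0.4, 0.4, 0.4).

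- Drug by Session: mean d = 0.30, Σ(d − mean)² = 0.12, λ = 25 × 0.12 / (1 − r) = 3 / (1 − r), on 3 and 294 df.
- Drug main effect: the variance of a subject's four-session mean is (1 + 3r)/4, so λ = 0.30² / [(2/50)(1 + 3r)/4], on 1 and 98 df.

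| r | λ, Drug by Session | Missed | λ, Drug | Missed |
|---|---|---|---|---|
| 0.5 | 6.0 | 48.8% | 3.60 | 53% |
| 0.7 | 10.0 | 24.5% | 2.90 | 61% |
| 0.8 | 15.0 | 8.7% | 2.65 | 64% |
| 0.9 | 30.0 | 0.2% | 2.43 | 66% |

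Higher correlation helps the interaction and hurts the main effect.

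**3. Loss growing evenly to 0.4 SD at week 3**, d = (0, 0.133, 0.267, 0.4). Here mean d = 0.20 and Σ(d − mean)² = 0.0889. Drug by Session misses it in 61%, 39%, 20% and 1.5% of trials; the Drug main effect misses it in 76%, 80%, 81% and 82%.

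**4. Baseline-adjusted difference at week 3.** SE = √[(1 − r²) × 2/50]; the 95% half-width is t(0.975, 97 df) × SE = 1.985 × SE.

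| r | SE (SD) | 95% half-width (SD) | 0.4 SD loss missed | Margin cleared in 80% of trials if true loss is 0 (SD) |
|---|---|---|---|---|
| 0.5 | 0.173 | 0.34 | 37% | 0.49 |
| 0.7 | 0.143 | 0.28 | 21% | 0.40 |
| 0.8 | 0.120 | 0.24 | 9% | 0.34 |
| 0.9 | 0.087 | 0.17 | 0.5% | 0.25 |

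The miss rate here is the same for both loss patterns, because only baseline and week 3 enter. The last column (one endpoint, one-sided 0.025) shows what size of bound 50 per group could support.

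**The case against.** The strongest reply is that the SAP sets out a search for harm, and a sensible one. It frames the test as being about loss, keeps the two strength outcomes separate, and shows concern for Type II error in the neighbouring outcomes. That stands, and the rmANOVA should stay.

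A reader might infer that the sponsor will treat a non-significant test as proof of preserved strength. The documents do not say so; they are silent on how such a result will be read. A reader might also infer that no rule exists anywhere. That goes too far: the wording of the second hypothesis is not in the supplied text, and the SAP points to an Aim 2 analysis that is not supplied either. The point is limited to what the supplied text contains.

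Nor do the figures show that this trial is weak at detecting a loss. With the interaction as the deciding term, the miss rate runs from 61% to 0.2% depending on r and on the shape of the loss, and it falls further for a larger loss: at 0.5 SD present at weeks 1 to 3 it is 28%, 7.5%, 1.1% and under 0.1%. Without r, no one can say where in that range the trial lies.

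Finally, a week-3 contrast is one reasonable estimand among several, and a fixed margin is open to debate. Both are fair. What survives is that neither term of the rmANOVA bounds the loss, and that the deciding term is unnamed.

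**Conclusion.** The concern holds in this form: in the supplied text, the strength half of Aim 1 is examined only by difference tests, which can signal harm but cannot bound a loss, and the term that decides is not stated.

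The choice of term is not a detail. At an assumed r of 0.9, the same 0.4 SD loss at weeks 1 to 3 is missed in 0.2% of trials by Drug by Session and in 66% by the Drug main effect. At r = 0.5 the two are close (49% and 53%), and both are weak. A high correlation therefore reassures only if the interaction is fixed in advance as the deciding term.

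These sizes rest on the assumed correlations, compound symmetry, 50 completers per group and an illustrative loss. The absence of a bound does not depend on any of them. This should be corrected, but it does not threaten the primary endpoint.

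**What to change.** - For flexion and for extension torque, report the baseline-adjusted cyproheptadine minus placebo difference at week 3 with a two-sided 95% confidence interval. The Protocol's Outcome Measures section already schedules that session: "and after one week at the highest dosage of up to 24 mg per day".
- Keep the rmANOVAs and name Drug by Session as the harm test.
- Base any conclusion that strength is not compromised on the lower confidence limits. If the sponsor can justify an acceptable loss, fix it before unblinding and compare the limits with it. If not, report that no loss was detected and that losses up to the confidence limit are not excluded.

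**Cost.** SAP wording and, if a margin is used, the work of justifying it. No extra patients, visits or procedures. The downside is that the no-loss claim becomes harder to make. At r = 0.5, a margin below about 0.5 SD would be cleared by one endpoint in fewer than 80% of trials even with no true loss; at r = 0.9 the corresponding figure is about 0.25 SD.
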